3.5 Insulin and glucose responses to food consumption

Following food consumption, absorbed carbohydrates give a rise in blood glucose concentrations. In response insulin is released causing blood glucose to fall. Different food components evoke different responses e.g. simple sugars give both rapid increases and falls. Glucose response refers to the degree of rise and fall in blood glucose levels and the time interval within which it occurs. Slowly digestible carbohydrates show a slower and more prolonged increase in blood glucose levels (with a lower peak) and vice versa. The glycemic index (GI) shows the average glucose concentration in the blood after consumption of a certain food (usually for 2 hours) relative to a standard food. The test foods usually contain 50 grams (or 25 grams if portion size is very large) of available carbohydrate and the reference food (anhydrous glucose powder, 50g or dextrose, 55g) has a GI of 100 [45]. Available carbohydrate of a food is estimated by difference: $100 - \text{water (g/100 g EP)} - \text{total fat (g/100g EP)} - \text{total protein (g/100 g EP)} - \text{total dietary fibre (g/100 g EP)} - \text{ash (g/100 g EP)}$. The GI is obtained from the area under the 2hour curve (iAUC)¹ [46] as:

$$\frac{\text{iAUC of the test food}}{\text{individual subjects/average iAUC of the reference food}} * 100$$
. Overall GI is calculated as mean (\pm SEM) GI value for ≥ 10 participants. From the GI, the glycaemic load (GL) can be derived. It is calculated

¹ The incremental area under the curve has been calculated as the incremental area under the blood glucose response curve (iAUC), ignoring the area beneath the fasting concentration. This can be calculated geometrically by applying the trapezoid rule. When a blood glucose value falls below the baseline, only the area above the fasting level is included.

as: $\frac{GI}{\text{Total available carbohydrate in the food portion}}/100$. GI gives information on glycaemic quantity as a factor of food portion size, and may be used as an indicator of insulin demand.

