The GI of the food will be measured over a 120 min period starting at the ingestion of the common bean product. The test food and reference food will be assessed in each subject on separate days with a 1 week period between each study day.

The GI value of the common bean product will be calculated as follows: = [iAUC of the common bean product/individual subject's average iAUC of reference food]*100. The overall GI will then be obtained as: The mean GI value for the 10 participants.

The test conditions, sample size and methodology are as adopted from the international standard ISO 26642:20110(E)³ [53].

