7.4 GI and FII study procedures

Researchers will obtain signed consent from the participants before testing. For the GI and FII study, the common bean product will be served with a standard 250 ml portion of water. Participants will first receive the reference food and then the test food on separate mornings after a 10-12h overnight fast. The conditions and testing times during the test days will be as similar as possible. Participants will be asked beforehand to maintain their usual diet; avoid alcohol; and not engage in unusual or excessive physical activity on the day preceding the test. For the night preceding the test day, participants will be asked to eat a standard evening meal that allows for the 10h fasting period prior to the study and refrain from eating and/or drinking (except for water).

On the test day, arrival time to the hospital will be 0700h. The researchers will assist participants in filling out a 24 hour dietary recall. Anthropometric measurements (weight, height, waist and hip circumferences); blood pressure; and body composition using bioelectrical impedance analysis (BIA) will be assessed. The subsequent tests will be conducted while the participants are in a rested position. A catheter will be introduced in the cubital vein to obtain venous blood by a phlebotomist. Two blood samples will be obtained within a five minutes interval in the fasting state, and their average taken as the baseline blood glucose concentration (time -5 and time 0). Participants will then be given the test food and 250ml water all presented in standard bowls and/or glasses. Participants will be asked to eat the whole portion in 12 to 15 minutes, at an even pace. Time taken to eat the entire portion will then be recorded. Participants will remain seated and will be allowed to read or use their phones. They will however not be allowed to sleep or eat or drink until the end of the 2h of study period.

[figure not shown]
Postprandial blood samples will be collected after the feeding at six time-points, 15, 30, 45, 60, 90 and 120 min. For each time point, ~2 ml of blood will be obtained. Whole-blood samples will be labelled using codes allocated to each participant for proper identification. Blood glucose content will be measured in either whole blood or plasma samples. Centrifugation will be done within 30 minutes of blood collection using portable centrifuges carried to the field. Blood plasma or serum

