8. DATA COLLECTION

8.1 Data collection processes

Glycemic index and glycemic response (*Appendix 2*)

- a. Equi-carbohydrate (50g or 25g) portions of the common bean product
- b. 24-hour of dietary recall
- c. Anthropometry: weight, height, waist & hip circumference
- d. Body composition: BIA
- e. Biochemical samples: Blood

Food insulin index (FII) and insulin response (*Appendix 2*)

- a. Iso-caloric (240kJ) portions of the common bean product
- b. 24-hour of dietary recall
- c. Anthropometry: weight, height, waist & hip circumference
- d. Body composition: BIA
- e. Biochemical samples: Blood

Appetite scores (*Appendix 3*)

- a. Visual analog scales
- b. Timers

BIA will be assessed with the Bodystat 500 (Bodystat, UK). Raw data on impedance, resistance, reactance and phase angle will be added to already validated equations to calculate fat free mass, body fat and hydration [56].

For blood draw, handling and processing; phlebotomists from the Kenya Medical and Research Institute (KEMRI) will be engaged. A catheter will be placed in the cubital vein. Blood samples will be collected at seven time-points; 0, 15, 30, 45, 60, 90 and 120 minutes. For each bleeding moment ~2 ml of blood will be drawn from the participant. Plain tubes will be used for blood collection. After collection, whole-blood samples will be labelled with codes with participant

codes and separated based on time-collection point. A drop of blood will then be obtained for determination of haemoglobin concentration using the Hemocue 301 portable device. The tubes will then be placed immediately into insulated coolers containing ice/cold packs at around 4°C awaiting centrifuging. Centrifuging will be within 30 minutes of sample collection. After centrifuging, serum will be separated and divided in aliquots. Cryovials containing the aliquots will be labelled (with participant code and test to be run), wrapped with aluminum foil (to reduce chances of light degradation) and secured together with rubber bands. They will then be put in a portable freezer. At the end of sample collection and separation, the aliquots will be dropped into a liquid nitrogen tank awaiting transportation to analytical laboratories (LANCET), for further analysis. Necessary precautions will be taken to ensure a dust and light free environment during the blood sample collection and handling.

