9.2 Glycemic and insulineric tests

Allowable mean within-subject co-efficient of variance (CV) for the reference food is $\leq 30\%$. The laboratory's inter-assay analytical variation on standard solutions should be $< 3.6\%$. The laboratory's minute-to-minute analytical variation in human subjects for 20 or more duplicate measurements of fasting glucose should generally be $< 5\%$. Glycemic and insulineric responses will be obtained from the iAUC (incremental area under the curve). iAUC is calculated by applying the trapezoid rule (sums of the areas of the triangles and trapezoids) [53]. iAUC is reported in millimole minutes per litre. Below is an example to how the iAUC and GI will be arrived at:

Table 2: Sample blood glucose responses to the ingestion of a 50g carbohydrate portion

| Food sample | Time of sampling, min | | | | | | | iAUC |
|----------------------------|-----------------------|-----|-----|-----|-----|-----|-----|------|
| | 0 | 15 | 40 | 45 | 60 | 90 | 120 | |
| Reference food replicate 1 | 4.3 | 6.3 | 7.9 | 5.3 | 4.1 | 4.6 | 4.9 | 114 |
| Reference food replicate 2 | 4.0 | 6.0 | 6.7 | 5.5 | 5.3 | 5.0 | 4.2 | 155 |
| Test food | 4.0 | 5.0 | 5.8 | 5.4 | 4.8 | 4.2 | 4.4 | 93 |

The iAUC for the Reference food replicate 1 = sums of the areas of the triangles and trapezoids A to F obtained after plotting the blood glucose responses at the different time intervals on a graph (Fig. 4).

Key

- c_{Glc} blood glucose
- r' horizontal side of triangle D
- r'' horizontal side of triangle E

Figure 4: Graph of blood glucose responses to the ingestion of a 50g carbohydrate portion over a 2h period

Calculation for GI

- Mean iAUC for the reference food= (iAUC reference food replicate 1+ iAUC reference food replicate 2)/ 2= 135±29 mmol min/l
- The CoV is thus $29/135*100 = 22\%$ (Test condition: CV for the reference food for the group should be $\leq 30\%$).
- iAUC for test food is 93 mmol min/l. For this subject, GI of the test food is thus $93/135*100 = 69\%$.

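### The glucose baseline is the mean of two fasting draws in section 7.4, but section 8.1 collects one fasting draw and the glucose assay budget matches one

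*Combined protocol and SAP*

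**What the plan says.** **Fasting draws.** Section 7.4 places two fasting samples at -5 and 0 min: "Two blood samples will be obtained within a five minutes interval in the fasting state, and their average taken as the baseline". It then adds: "Postprandial blood samples will be collected after the feeding at six time-points, 15, 30, 45, 60, 90 and 120 min". Section 8.1, which describes the phlebotomists' work, says: "Blood samples will be collected at seven time-points; 0, 15, 30, 45, 60, 90 and 120 minutes". It has no -5 min sample. The two-draw rule in 7.4 is given for glucose; no insulin baseline is defined there.

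**Quality limit.** Section 9.2 says that the "minute-to-minute analytical variation in human subjects for 20 or more duplicate measurements of fasting glucose should generally be" below 5%.

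**Reference sessions.** Section 7.4 gives an order: "Participants will first receive the reference food and then the test food on separate mornings after a 10-12h overnight fast". Section 7.1 gives a spacing: "The test food and reference food will be assessed in each subject on separate days with a 1 week period between each study day". Neither these sections nor 7.2 gives the number of reference sessions. Sections 7.1 and 7.2 divide by each subject's average reference iAUC. Section 9.2 averages two reference replicates and limits the within-subject CV to 30%. Section 11 says that the reference is tested twice.

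**Budget (12.3).** Glucose and insulin each have 30 fasting and 180 non-fasting assays. Other lines give 200 blood tubes, 30 lunches over 3 days, and 4 days for most field staff.

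**The concern.** Sections 7.4 and 8.1 are both complete instructions, and they cannot both be followed. A team working from 8.1 takes one fasting sample, and the averaged baseline is then out of reach. The missed sample cannot be recovered once the session is over.

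The baseline carries much of the error in an iAUC, because the same fasting value is subtracted at every later time-point. An error in it does not average out over the curve. It also enters the GI through both the test and the reference curves.

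The unstated number of reference sessions is a smaller matter of the same kind. One reference morning would satisfy the order in 7.4 read alone, and a within-subject CV cannot be computed from one value.

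**Working it through.** **1. Draws per session.**
- 7.4: 2 fasting + 6 postprandial = 8.
- 8.1: 1 fasting + 6 postprandial = 7.
- Glucose line in 12.3: 30:180 = 1:6. This fits one fasting draw per session whatever the number of sessions; 7.4 needs 2:6.
- 180/6 = 30 sessions, and 30 x 7 = 210 reproduces the budgeted total. With the -5 min draw, 30 x 8 = 240, so 30 assays are missing.

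**2. The plan's own example (9.2, Table 2).** The trapezoid rule above the fasting level, with the third time-point taken as 30 min, gives iAUCs of 114.0, 155.2 and 93.0. The table prints 40 min, but only 30 reproduces its values. Using the printed 114 and 155, the mean is 134.5, the SD 29.0 and the CV 21.6%. GI = 93/134.5 x 100 = 69.

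**3. Effect of the second fasting draw.** Assume an error SD of 5% of the fasting value per draw (the limit in 9.2), independent between draws, with the curve starting at the baseline. The trapezoid weights of the six later points are 15, 15, 15, 22.5, 30 and 15 min, which sum to 112.5 min. While the curve stays above baseline, an error of e mmol/L therefore moves the iAUC by 112.5e.
- One draw: 0.05 x 4.0 = 0.20 mmol/L; 112.5 x 0.20 = 22.5.
- Two draws: 22.5/√2 = 15.9.

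Simulation (40,000 replicates), which also handles values below baseline, agrees. For GI, the error is applied to all three example sessions. Each mean of 10 is the one-subject SD divided by √10.

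| Error SD | Quantity | One draw | Two draws |
|---|---|---|---|
| 5% | Test iAUC, one subject (mmol.min/L) | 21.9 | 15.7 |
| 5% | Test iAUC, mean of 10 | 6.9 | 5.0 |
| 5% | GI points, one subject | 18.4 | 13.1 |
| 5% | GI points, mean of 10 | 5.8 | 4.1 |
| 2.5% | Test iAUC, one subject (mmol.min/L) | 11.2 | 7.9 |
| 2.5% | GI points, mean of 10 | 2.9 | 2.1 |

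**4. Reference sessions.** With one reference in the same example, GI would be 93/114 = 82 or 93/155 = 60 instead of 69, and no within-subject CV would exist.

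**5. Sessions against the 210 assays for each analyte.** These counts assume that GI and FII share sessions, with two fasting glucose draws and one fasting insulin draw.

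| Design | Sessions | Glucose assays | Insulin assays |
|---|---|---|---|
| Healthy: 2 reference + 1 test; T2DM: none | 30 | 240 | 210 |
| Healthy: 2 reference + 1 test; T2DM: 1 test | 40 | 320 | 280 |
| All 20: 2 reference + 1 test | 60 | 480 | 420 |

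Cost of 10 further sessions, making 40:
- Glucose: 110 x 649 = 71,390.
- Insulin: 10 x 3,849 + 60 x 4,149 = 287,430.
- Lunches: 10 x 500 = 5,000.
- Tubes: 320 needed, two more packs, 2 x 1,200 = 2,400.
- Sum: KSh 366,220; 366,220/1,653,775 = 22.1%.

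At 60 sessions the assays alone add 270 x 649 + 30 x 3,849 + 180 x 4,149 = KSh 1,037,520 (62.7%).

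**The case against.** **On the draws.** A figure is missing from the available text of 7.4, just before the postprandial draws, and may show the -5 min sample. It would not remove the conflict with the list in 8.1. The 5% is an acceptance ceiling, and every mean of 10 repeats one illustrative subject. That stands: the table in step 3 shows the size under stated conditions and is not a forecast.

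**On the reference sessions.** A reader might infer that the plan intends a single reference session, or contradicts itself on it. The documents do not support that. Sections 9.2 and 11 commit to two, 7.1 and 7.2 divide by an average, and 7.1 adopts the ISO method. The gap is an unstated number in section 7.

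**On the budget.** A reader might also infer that the laboratory lines cannot pay for two reference tests. That goes too far. The 30 assayed sessions hold two references and one test in all 10 healthy volunteers, the group in which GI and FII are determined. They fall short once T2DM sessions are assayed. Four field days at 10 people a day (an assumption taken from 30 lunches over 3 days) give 40 sessions, which fits two references plus one test in healthy volunteers and one test in T2DM patients. The budget lines disagree with one another and are not a visit schedule, so any session count is inferred.

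**On adding the effects.** Baseline error of 5% with one draw alone gives a CV of about 14% to 18% in the two example reference iAUCs. It would already be part of the within-subject CV that replicate references address. The two magnitudes overlap and must not be summed.

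**Conclusion.** The fasting-draw conflict is real and wrong as written: eight draws in 7.4, seven in 8.1, and a glucose budget that matches seven. One draw instead of two raises the baseline error SD by a factor of about √2. At the plan's 5% ceiling that is about 22 against 16 mmol.min/L in the example test iAUC, and 5.8 against 4.1 GI points for a mean of 10 such subjects. At 2.5% the figures roughly halve. They assume independent errors and the curve shape of the plan's one example.

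The number of reference sessions and the budget are secondary consistency points. Intent on two references is settled by 9.2 and 11. The size of the budget gap depends on two things that the documents leave open: whether T2DM patients receive the reference food, and whether GI and FII, which use different portion definitions in 7.1 and 7.2, share sessions. The KSh 366,220 at 40 shared sessions is therefore a minimum for a study that includes T2DM sessions, not a ceiling. This should be fixed before the first session.

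**What to change.** **Main change.**
- In 8.1, add the -5 min draw, so that it lists eight time-points as in 7.4.
- State that the glucose baseline is the mean of -5 and 0, and say which draw or draws form the insulin baseline.
- Add the draw to the assay and tube counts.

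Cost in the 30 sessions now funded: 30 glucose assays x 649 = KSh 19,470 (1.2% of the grand total). Tubes rise to 240 against 200 budgeted, so one more pack is needed at KSh 1,200. The 200 tubes are already short of the 210 that seven draws require.

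**Consistency edits.**
- In 7.1, 7.2 and 7.4, state the two reference sessions that 9.2 and 11 assume, for every subject whose GI or FII is calculated. The wording is free. Against a literal one-reference reading of 7.4, each such subject attends one more fasting morning, a week apart.
- State whether T2DM patients receive the reference food (this review takes no view) and whether GI and FII share sessions.
- Reconcile the glucose, insulin, tube, lunch and study-day lines to the resulting count: at least about KSh 366,000 extra at 40 shared sessions, before any added field day, and about KSh 1,037,520 extra in assays at 60. Separate GI and FII sessions would raise both.

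No extra participants are needed.

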7.5 Appetite scores using Visual Analog Scales (VAS)

Appetite scores will be used to assess the satiety power of the test (common bean) product among T2DM participants. The appetite score will be taken on one study day, that is, after consumption of the bean product. Subjective measures of appetite will be taken prior to, and at predetermined time intervals after consumption of the test meal. Appetite score refers to the average between hunger, desire to eat, prospective consumption and a 100-fullness score. The appetite score will be assessed at before and after consumption of test product at time points 0, 15, 30, 45, 60, 90 and 120 minutes. Participants will be given a short questionnaire to assess satiety.

A single vertical mark best expressing the participants' response will be made on an anchored 100 mm VAS scale. The anchor on the left and right will express the most positive and the most negative rating respectively (see Appendix 7). The response will be quantified by measuring the distance between the left anchor and the marking made. The questionnaires will be made as a small brochure booklet showing one question at a time [54][55]. Participants will be asked to remain silent while filling out their VAS. Between evaluations, they will be allowed to read or use their phones. The participants will not be allowed to discuss with each other or refer to previous ratings when filling out the VAS.

Blood draw + Appetite scores

Figure 3: Summary of protocol for the assessment of postprandial glycemic, insulinemic and satiety responses

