6. HYPOTHESES AND RESEARCH QUESTIONS

6.1 Hypotheses

H1: the new common bean product is not associated with desirable satiety, glyceimic and insulimemic responses in the T2DM patients.

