6.2 Research questions

1. What are the post prandial insulin, blood glucose and appetite responses associated with consumption of the common bean product in:
 - a. healthy volunteers?
 - b. T2DM patients?

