9.3 Appetite scores

Averages of markings on the VAS for all the participants will be calculated. Descriptive data will be expressed as means and/or standard errors or deviations. Cronbach's alpha will be used to assess validity of the appetite scores. ANOVA, Tukey's significant difference test and Pearsons correlation will be used to analyze the effects of product consumption and composition on appetite scores and to assess the repeatability.

Data will be coded, entered and analysed using either/or SPSS, R, Excel or STATA software.

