11. STUDY LIMITATIONS AND RISKS

Limitations include assessment of one test product. Additionally, when determining the GI and FII, a limitation is in the inter-individual, day-to-day, and even within-day variance in glycemic and insulinemic response to a particular food. For this, we will adhere to recommendations from the ISO 26642:2010 (e.g. testing the reference food twice to reduce day-to-day variability within individuals, follow recommendations as in protocol section 9.2 among other guidelines).

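### Appetite is scored on one bean day, among T2DM participants only, so the composition and repeatability analyses in Section 9.3 cannot be estimated and the appetite part of question 1a has no scheduled data

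*Combined protocol and SAP*

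**What the plan says.** Section 7.5 gives the purpose and the population: "Appetite scores will be used to assess the satiety power of the test (common bean) product among T2DM participants". It then limits the measurement: "The appetite score will be taken on one study day, that is, after consumption of the bean product". Ratings are taken at seven times from 0 to 120 minutes. Sections 7.1 and 7.2 give 10 T2DM patients and 10 healthy volunteers.

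Section 11 states: "Limitations include assessment of one test product".

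For the analysis, Section 9.3 lists ANOVA and Tukey's test and continues: "Pearsons correlation will be used to analyze the effects of product consumption and composition on appetite scores and to assess the repeatability". On Cronbach's alpha it says "alpha will be used to assess validity of the appetite scores"; Section 8.5 lists the same statistic under reliability.

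Section 6.2 asks "What are the post prandial insulin, blood glucose and appetite responses associated with consumption of the common bean product in" (a) healthy volunteers and (b) T2DM patients. H1 in Section 6.1 is worded as a null for the T2DM patients and begins "the new common bean product is not associated with desirable satiety". It goes on to the glucose and insulin responses.

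**The concern.** The analysis section promises results that the data collection section cannot supply. An effect of composition needs at least two compositions. Repeatability needs at least two sessions in the same person. Neither is planned for appetite.

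What remains is a before-after change on one day in people who arrive after a 10-12 hour fast. Without an appetite score on any other food, a fall in the score could be reported as the product's satiety power when it may only reflect having eaten.

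The appetite part of question 1a is also at risk. If healthy volunteers attend and are not scored, those data cannot be recovered afterwards.

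**Working it through.** The plan gives no sample size, precision or power figure for appetite, so there is none to reproduce. The check is one of estimability.

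**Inputs.** 10 T2DM participants (Sections 7.1, 7.2); 1 scored day and 7 time points (Section 7.5); 1 product (Section 11).

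**Planned data.** 10 × 1 × 7 = 70 scores. A model with intercept, participant and time has rank 1 + 9 + 6 = 16.

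| Planned effect | Degrees of freedom added | Consequence |
|---|---|---|
| Composition (or meal) | 1 level − 1 = 0 | Not estimable; a correlation with a constant is undefined |
| Repeatability (participant by day) | 0, because day coincides with participant | Not estimable |
| Consumption, as change from time 0 | 6 (time, already in the model) | Estimable, without a control |

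The seven times within a day cannot stand in for replicates, because appetite is expected to change after eating. Cronbach's alpha can be computed, but it measures agreement between items. The documents do not offer it as a measure of repeatability across sessions.

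**What other designs would give.** A scored reference day alongside the bean day gives 140 scores, 1 df for meal and 10 df for participant by day. A second bean day instead gives 10 df for repeatability but still 0 for composition.

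**Precision of what can be estimated.** The 95% half-width for a mean change in 10 people is t(0.975, 9) × SD/√10 = 2.262 × SD/3.162 = 0.715 × SD. For an assumed SD of change of 15, 20 or 25 mm this is 10.7, 14.3 or 17.9 mm. The documents give no SD.

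**How little a significant fall would show.** Suppose that any meal lowers the score and the bean product adds nothing of its own. The chance that a one-sample t test on the change (n = 10, two-sided 5%) is significant depends on assumed values:

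| Assumed fall (mm) | SD 15 | SD 20 | SD 25 |
|---|---|---|---|
| 5 | 16% | 11% | 9% |
| 10 | 47% | 29% | 21% |
| 15 | 80% | 56% | 40% |
| 20 | 96% | 80% | 62% |
| 30 | over 99.9% | 99% | 92% |
| 40 | over 99.9% | over 99.9% | 99% |

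This is ordinary power for a real post-meal change, not a false-positive rate. The range, about 9% to over 99.9%, is too wide to carry the argument. The argument rests on the missing comparator.

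**Healthy volunteers.** Section 7.5 is the only place that names a scored population, and it names T2DM participants. Section 9.3 averages the VAS marks over all participants, Section 8.1 lists appetite scores without naming a group, and the contents list puts satiety in the titles of both consent forms. None of these schedules a rating in healthy volunteers.

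**The case against.** The strongest reply is that the aim is descriptive. The general objective and question 1 ask for responses associated with eating the product, and the introduction speaks of product profiling. A seven-point profile in T2DM patients answers question 1b without a comparator, and Section 11 already discloses the single product. This stands for question 1b. It does not rescue composition or repeatability: Section 11 does not withdraw them and does not mention the lack of a repeat session or of an appetite comparator.

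A second reply is that healthy volunteers may be meant to be scored, given the wording of Sections 9.3 and 8.1. A reader might infer from Section 7.5 that it is settled that none will be. The documents do not support that: they conflict, and the consent forms and figures are not in the text available. What can be said is that no healthy scoring is scheduled.

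A reader might also infer from the budget that T2DM patients have no reference session. There are 210 glucose tests, and 210/7 = 30 sessions, matching 30 lunches over 3 days; 10 × 2 + 10 × 1 = 30 would fit healthy volunteers on two foods and T2DM patients on one. But the same budget lists 4 study days, 80 needles and 80 IV tubes. At 10 people a day, 4 days give 40 sessions, which equals 20 × 2. Section 7.4 also adds a draw at −5 minutes, and 210/8 = 26.25 is not a whole number of sessions. The budget contradicts itself and cannot settle the matter.

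Finally, the word desirable is as undefined for the glucose and insulin parts of H1 as for satiety. The satiety part differs in having no reference-food measurement planned at all.

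**Conclusion.** The point holds. As written, two analyses in Section 9.3 have no data behind them: 0 degrees of freedom for composition and one session per person for repeatability. This follows from the text and needs no assumed value.

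The consumption effect is estimable as an uncontrolled change from time 0. It is sound as a description of the T2DM response and unsound as evidence about the bean product specifically. The satiety part of H1 has neither a comparator nor a threshold, so it cannot be presented as tested. The appetite part of question 1a has no scheduled data, and Sections 7.5 and 9.3 conflict on who is scored.

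It would go too far to say that the T2DM profile is worthless or that the glucose and insulin analyses are affected by this point. The millimetre half-widths and the percentages rest on assumed SDs and meal effects. Correcting Section 9.3 is needed; scoring the healthy volunteers is a cheap improvement.

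**What to change.** 1. **Section 9.3.** Delete composition and repeatability. Analyse the scores as a repeated-measures time profile: mean change from time 0 at each post-meal time with 95% confidence interval, time as a fixed effect and participant as a random effect. Report it as descriptive and uncontrolled. Call Cronbach's alpha internal consistency. Do not present the satiety part of H1 as tested.

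2. **Question 1a and Section 7.5.** Give the VAS booklet to healthy volunteers at the bean and reference sessions they already attend. Report the bean profile and the paired bean-minus-reference difference (one summary value per person per session, for example the time-weighted mean change from time 0) with 95% confidence interval, descriptively. For an assumed SD of the difference of 10, 15 or 20 mm, the half-width with n = 10 is 7.2, 10.7 or 14.3 mm. State two downsides: a glucose drink is an imperfect comparator for satiety, and Section 7.4 gives the reference first, so food is confounded with visit order. Otherwise, delete appetite from question 1a. Either way, make Sections 7.5 and 9.3 agree on who is scored.

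3. **T2DM reference session.** Reconcile Sections 7.1, 7.2, 7.4, 11 and 12.3 on whether T2DM patients have one. Section 11 also promises "testing the reference food twice to reduce day-to-day variability within individuals" without saying in which group. If T2DM reference sessions exist, score appetite there too and report the same paired difference.

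**Cost.** Step 1 and the reconciliation are text changes. Step 2 needs 10 × 2 = 20 more booklets, or 10 × 3 = 30 if the reference is tested twice, and more if the GI and FII tests use separate days. If the KSh 500 paper line covers the 10 booklets now planned (an assumption, KSh 50 each), that is KSh 1,000 to 1,500 for 20 to 30 booklets, plus a few minutes per session. No new visits or blood draws are needed. Section 8.6 seeks ethics committee approval for all data collection procedures and tools, so the added scoring would have to be included there.
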